8.3.10 Reporting of Pregnancy

Pregnancy is not an AE. However, any pregnancy that occurs following the booster dose (through three months after booster dose or through 12 months after the mRNA-1272.211

booster dose) should be reported to the sponsor on the appropriate DCF Pregnancy form and pregnancy should be followed to outcome.

8.4 Unanticipated Problems

8.4.1 Definition of Unanticipated Problems (UPs)

The Department of Health and Human Services (DHHS) OHRP considers unanticipated problems involving risks to subjects or others to include, in general, any incident, experience, or outcome that meets all of the following criteria:

- Unexpected in terms of nature, severity, or frequency given (a) the research procedures that are described in the protocol-related documents, such as the IRB-approved research protocol and informed consent document; and (b) the characteristics of the subject population being studied;
- Related or possibly related to participation in the research (“possibly related” means there is a reasonable possibility that the incident, experience, or outcome may have been caused by the procedures involved in the research); and
- Suggests that the research places subjects or others at a greater risk of harm (including physical, psychological, economic, or social harm) than was previously known or recognized.

8.4.2 Unanticipated Problem Reporting

To satisfy the requirement for prompt reporting, UPs will be reported using the following timeline:

- UPs that are SAEs will be reported to the IRB and to the SDSU/study sponsor within 24 hours of the participating site PI or appropriate sub-investigator becoming aware of the event per the above-described SAE reporting process.
- UPs that are SAEs will be collected from Day 1 through the end of planned study participation.
- Any other UP will be reported to the IRB and to the SDSU/study sponsor within 3 days of the participating site PI or appropriate sub-investigator becoming aware of the problem.
- UPs that are not SAEs will be collected from Day 1 through 28 days after last vaccination.

8.4.3 Reporting Unanticipated Problems to Subjects

Subjects will be informed of any UPs that occur as part of their participation in this trial.

9 STATISTICAL CONSIDERATIONS

9.1 Statistical Hypotheses

This is a phase 1/2, open-label, multi-site clinical trial that is not designed to test a specific hypothesis. Rather, it is intended to obtain preliminary estimates in healthy adults of the safety, reactogenicity, and immunogenicity of delayed heterologous SARS-CoV-2 vaccine dosing (boost) after receipt of EUA vaccines.

9.2 Sample Size Determination

9.2.1 Sample Size Calculation for the Safety Endpoint

Rare AEs are not demonstrable in a clinical study of this size; however, the probabilities of observing one or more AEs given various true event rates are presented in Table 13. With the assumption that all enrolled subjects will likely complete immunizations and safety visits in this relatively short duration study, the following statistical considerations apply. With approximately 50 subjects in each group there is a 99.5% chance of observing at least one AE of probability 10%. Similarly, with approximately 25 subjects in each of the age subgroups, there is a 92.8% chance of observing at least one AE of probability 10%. Therefore, if no AEs of a given type occur in a Cohort 1 group, we can be relatively confident that they will occur in fewer than 10% of people once the vaccine is implemented.

Probabilities of observing one or more AEs, assuming an attrition rate of approximately 10% (N = 45, N = 22), are also shown in Table 13.

Due to the surge in Omicron variant cases at the time of the writing of Version 6.0, it is anticipated that a non-negligible proportion of vaccinated individuals may be prone to asymptomatic breakthrough infections. To allow for potential larger numbers of participants enrolled in Stage 6 (Groups 15E-17E) that would subsequently be found to have serological evidence of prior infection, the sample size will be expanded to N = 60/group (approximately 1:1 age strata) for these groups.

9.2.2 Sample Size Calculation for the Immunogenicity Endpoints

A co-primary objective of this study is to evaluate the magnitude of SARS-CoV-2 specific antibody titers in serum samples. This objective is descriptive in nature and will be accomplished by estimating 95% confidence intervals (CI) for the geometric mean titer (GMT) at each timepoint when samples are collected.

Table 13: Probability of Observing an Adverse Event for Various Event Rates in one vaccine schedule group (or age subgroup), assuming no attrition (N = 50 or N = 25) or approximately 10% attrition (N = 45 or N = 22).

N	“True” Event Rate	Probability of Observing ≥ 1 events (%)	N	“True” Event Rate	Probability of Observing ≥ 1 events (%)
50	0.1%	4.9	45	0.1%	4.4
	0.5%	22.2		0.5%	20.2
	1.0%	39.5		1.0%	36.4
	2.0%	63.6		2.0%	59.7
	3.0%	78.2		3.0%	74.6
	4.0%	87.0		4.0%	84.1
	5.0%	92.3		5.0%	90.1
	10.0%	99.5		10.0%	99.1
	15.0%	>99.9		15.0%	99.9
	20.0%	>99.9		20.0%	>99.9
30.0%	>99.9	30.0%	>99.9		
N	“True” Event Rate	Probability of Observing ≥ 1 events (%)	N	“True” Event Rate	Probability of Observing ≥ 1 events (%)
25	0.1%	2.5	22	0.1%	2.2
	0.5%	11.8		0.5%	10.4
	1.0%	22.2		1.0%	19.8
	2.0%	39.7		2.0%	35.9
	3.0%	53.3		3.0%	48.8
	4.0%	64.0		4.0%	59.3
	5.0%	72.3		5.0%	67.6
	10.0%	92.8		10.0%	90.2
	15.0%	98.3		15.0%	97.2
	20.0%	99.6		20.0%	99.3
30.0%	>99.9	30.0%	>99.9		

The precision with which the GMT can be estimated from observed data depends on the standard deviation (SD) of the measurements, on the logarithmic scale, and the sample size. Table 14 displays two-sided 95% confidence intervals for the GMT for several values of the observed antibody titer. Table 14 also shows results assuming up to 10% attrition.

Table 14: Two-sided 95% confidence intervals based on observing a particular average log_e-antibody titer in subjects' vaccine groups and age subgroups.

Observed average log _e antibody titer	SD of log _e antibody titer	95% confidence interval of GMT in vaccine group		95% confidence interval of GMT in age subgroup	
		N = 50	N = 45*	N = 25	N = 22*
log _e (5)	0.5	(4.3, 5.8)	(4.3, 5.8)	(4.1, 6.1)	(4, 6.2)
log _e (20)		(17.4, 23.1)	(17.2, 23.2)	(16.3, 24.6)	(16, 25)
log _e (50)		(43.4, 57.6)	(43, 58.1)	(40.7, 61.5)	(40.1, 62.4)
log _e (100)		(86.8, 115.3)	(86.1, 116.2)	(81.4, 122.9)	(80.1, 124.8)
log _e (250)		(216.9, 288.2)	(215.1, 290.5)	(203.4, 307.3)	(200.3, 312)
log _e (500)		(433.8, 576.3)	(430.3, 581)	(406.8, 614.6)	(400.6, 624.1)
log _e (1000)		(867.5, 1152.7)	(860.5, 1162.1)	(813.5, 1229.2)	(801.2, 1248.2)
log _e (5)	1.0	(3.8, 6.6)	(3.7, 6.8)	(3.3, 7.6)	(3.2, 7.8)
log _e (20)		(15.1, 26.6)	(14.8, 27)	(13.2, 30.2)	(12.8, 31.2)
log _e (50)		(37.6, 66.4)	(37, 67.5)	(33.1, 75.6)	(32.1, 77.9)
log _e (100)		(75.3, 132.9)	(74, 135)	(66.2, 151.1)	(64.2, 155.8)
log _e (250)		(188.2, 332.2)	(185.1, 337.6)	(165.5, 377.8)	(160.5, 389.5)
log _e (500)		(376.3, 664.3)	(370.2, 675.2)	(330.9, 755.5)	(320.9, 779)
log _e (1000)		(752.6, 1328.7)	(740.5, 1350.4)	(661.8, 1511)	(641.9, 1558)

* Assumes approximately 10% attrition.

9.3 Populations for Analyses

The safety analysis population includes all enrolled subjects who received at least one dose of study vaccine. Analyses for the safety population will include safety reported through the end of the study. The modified intent-to-treat (mITT) population includes all subjects who received at least one dose of vaccine and contributed both pre- and at least one post-vaccination venous blood sample for immunogenicity testing for which valid results were reported.

In the final analysis, protocol deviations will be reviewed to determine which protocol deviations may affect the analysis. The per protocol (PP) population will then be defined – and this includes all subjects in the mITT subset with the following exclusions:

- Data from all available visits for subjects found to be ineligible at baseline.
- Data from all visits subsequent to the protocol deviations that are considered to affect the science.
- Data from any visit that occurs substantially out of window.

9.4 Statistical Analyses

Interim analyses of safety, reactogenicity, and immunologic response data will be done, as needed.

The final analysis will be performed after the final data lock and clinical study report (CSR) completed when all primary safety endpoint data and all secondary immunogenicity endpoint data are available and received by the SDSU. The final CSR will be completed when all primary and secondary safety, clinical, and immunological endpoint data are available. Available data from the exploratory endpoints at the time of compilation of the final CSR may also be included. Other remaining exploratory endpoint data may be included in an addendum to the CSR, publication of manuscript(s), or other report(s). Abbreviated analysis plans that describe planned analyses to facilitate dissemination of study data for public health reasons, including manuscript publication(s), will be developed by the SDSU. A full statistical analysis plan (SAP) will be developed by the SDSU and finalized prior to the primary data lock.

9.4.1 General Approach

Unless otherwise noted in the SAP, continuous variables will be summarized using the following descriptive statistics: n (non-missing sample size), mean, standard deviation, median, maximum and minimum. The frequency and percentages (based on the non-missing sample size) of observed levels will be reported for all categorical measures.

9.4.2 Analysis of the Primary Endpoint(s)

[Section 9.4.4](#) describes the analyses of Safety Endpoints, which is one of the co-primary endpoints of this protocol.

9.4.3 Analysis of the Co-Primary Endpoint(s)

Descriptive summaries of immunogenicity data will be presented for the mITT population. If there are protocol deviations which may affect the analysis, a per-protocol (PP) analysis may also be performed.

Geometric Mean Titers (GMT) and Geometric Mean Fold Rise (GMFR) from baseline of SARS-CoV-2 specific antibody binding and neutralization titers will be calculated, along with 95% CIs, for all groups, at each timepoint. Summaries will also be displayed graphically. Rates of seroconversion, defined as a 4-fold increase in antibody titer over baseline, will also be reported for all groups, at each timepoint, along with 95% CIs.

9.4.4 Safety Analyses

Summaries and analysis of safety data will be presented for the Safety Analysis Population.

Solicited AEs will be summarized by severity for each day post vaccination (Days 1-8) and as the maximum severity over all 8 days. Additionally, solicited AEs will be analyzed using standard techniques, such as exact confidence intervals (CI), to summarize the proportion of subjects reporting each symptom, any application site symptom, and any systemic symptom.

Unsolicited non-serious AEs will be collected from the time of first vaccination through 28 days after the last vaccination. Unsolicited AEs will be coded by MedDRA for preferred term and system organ class (SOC). SAEs, Protocol Specified AESIs, MAAEs, and NOCMCs will be collected from the time of first vaccination to end of planned study participation. The numbers of SAEs, AESIs, NOCMCs and MAAEs will be reported by detailed listings showing the event description, MedDRA preferred term and SOC, relevant dates (vaccinations and AEs), severity, relatedness, and outcome for each event. Non-serious unsolicited AEs will be summarized as number and percentage of subjects reporting at least one event in each MedDRA preferred term and SOC, cross tabulated by severity and relationship to study product. Additionally, the proportion of subjects and exact 95% CIs of AEs in aggregate and by MedDRA categories will be computed.

9.4.5 Baseline Descriptive Statistics

Summaries of demographic variables such as age, sex, ethnicity, and race will be presented by cohort and overall. Summaries of baseline clinical laboratory values will be presented by arm and cohort.

9.4.6 Planned Interim and Early Analyses

Data may be disseminated to public health officials and partners as needed and included in publications and presentations to inform the global scientific community. Early analyses will include safety and immunogenicity as described in [Sections 9.4.6.1, 9.4.6.2 and 9.4.6.3](#). Further, the protocol team will review data periodically to confirm no halting criteria have been met as described in [Section 10.1.6.1](#).

Cumulative safety information, study status, and primary endpoint results may be published, presented at a public forum, or presented as summaries aggregated by study arm at the discretion of the sponsor while the study is ongoing. Any ad-hoc analyses jointly developed by the study team and SDSU will be executed by the SDSU and SCHARP as needed. None of the interim

analyses will include any formal statistical hypothesis testing; therefore, p value adjustment will not be made to any analyses.

9.4.6.1 Interim Safety Analyses

Given the need for rapid review and dissemination of study data for public health reasons, AEs and SAEs may be reviewed as necessary outside of SMC reviews. The SMC may not need to meet (unless halting rules are met), and materials will be provided electronically. Documentation of review and any concerns noted will be solicited electronically.

The SMC will review separate cumulative AE data reports after all subjects within each booster product group have been dosed and completed Day 29 within Cohort 1. At the time of the writing of Version 8.0 of the protocol there are no scheduled mandatory reviews by the SMC after participants in Cohort 2 receive the prime, first boost or second boost vaccinations. This is due to the safety database known for EUA vaccines and vaccinations being administered in accordance to CDC guidelines. SMC reviews for Cohort 2 will occur if halting rules are triggered, or as requested by the sponsor or PI.

9.4.6.2 Interim Immunogenicity Review

Interim data review of immunogenicity will be performed as often as needed to inform public health decisions.

Statistical analyses of secondary immunogenicity endpoints, by vaccine schedule group, may be performed when subjects have completed key immunogenicity visits. Immunogenicity reviews may be shared with the SMC, as determined by DMID.

Data may be disseminated to public health officials and partners as needed and included in publications and presentations to inform the global scientific community.

9.4.6.3 Interim Immunogenicity and Safety Review

Interim analyses of safety, reactogenicity, and immunologic response data may be done, as needed.

9.4.7 Sub-Group Analyses

Subgroup analyses, by age group, may be performed. For group 15E, which will enroll participants with one or two prior doses of Janssen, a subgroup analysis by this baseline characteristic may also be performed. Detailed information will be provided in the Statistical Analysis Plan.

9.4.8 Tabulation of Individual Subject Data

In general, all data will be listed, sorted by arm and subject, and when appropriate by visit number within subject.

9.4.9 Exploratory Analyses

Summaries and analysis of cellular assay data will be presented for the mITT population. If there are protocol deviations which may affect the analysis, a PP analysis may also be performed.

The magnitude, phenotype and percentage of innate immune cells and SARS-CoV-2 specific B cells will be summarized at each timepoint by arm.

The magnitude, phenotype and percentage of cytokine producing S protein-specific T cells will be summarized at each timepoint by arm.

Breakthrough NAAT-confirmed, SARS-CoV-2 infections will be sequenced to assess for the presence of variant spike lineage proteins.

Summaries of mucosal immune responses, from nasal and salivary samples of participants in Cohort 2 who receive a second boost, will be summarized at each timepoint post-boost. Also, the correlation between the mucosal and the serological immune responses will be evaluated at each timepoint post-boost. The possibility of conducting these analysis by status of prior infection (as given by N-protein ELISA assay) will be assessed.

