Prospective Cohort: Cohort 2 will recruit persons who are naïve to COVID-19 vaccine and infection (by history). These individuals will be given a vaccine as part of the study that matches the vaccine/dose available under an EUA. Cohorts from this pool will then be available to be boosted with a novel homologous or heterologous variant lineage spike proteins or heterologous platform delayed boost as part of an adaptive design meant to respond quickly to circulating SARS-CoV-2 variants. As booster vaccines have been approved for individuals at an interval of 6 months from the primary series, under EUA, all Cohort 2 volunteers will be offered a booster of mRNA-1273 at the approved 50 mcg dose. Due to the surge of the Omicron variant and breakthrough infections, volunteers who contract symptomatic or asymptomatic COVID-19 between completion of their EUA primary series and the scheduled booster dose will be allowed to continue in the study. The interval between the COVID-19 infection and booster dosing should be a minimum of 28 days. This pool of participants will then be followed to assess the immunogenicity of a 4th dose of bivalent vaccine. The Moderna mRNA-1273.222 vaccine that contains 25-mcg of the prototype strain and 25-mcg of the Omicron BA.4/BA.5 variant (total 50-mcg) will be administered as a second booster 4 to 12 months after administration of the first booster vaccine.

Prioritization of Cohort 1 versus Cohort 2 enrollment will be determined by availability of EUA-dosed vaccines, status of distribution, and current epidemiology. Cohorts 1 and 2 may enroll simultaneously.

Table 2: Prospective Cohort 2

Group	Sam- ple Size*	First Vaccina- tion**	Inter- val	Second Vaccina- tion**	Inter- val	Delayed Booster Vaccina- tion 1	Interval	Booster Vaccination 2
1	250	Moderna- 100 mcg mRNA- 1273	28 days	Moderna- 100 mcg mRNA- 1273	~6 months	Moderna - 50 mcg mRNA- 1273	4-12 months	Moderna - 50 mcg mRNA- 1273.222

*Aged \geq 18 years

** As part of an adaptive design, products newly awarded EUA can be added as programmatically needed.

Duration of Study: Approximately 4 years

Duration of participation per subject: Up to 2 years (approximately ~6 months after second booster inoculation)

Criteria for Inclusion/Exclusion:

Inclusion Criteria:

Participants must meet all of the following criteria to be eligible to participate in this study:

1. Individuals \geq 18 years of age at the time of consent.

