SAEs, Protocol specified AESIs, MAAEs, and NOCMCs			X	X	X	X		X	X	X	X	X	X	X	X	X
Nasal or NP swab for PCR & Sequencing															X ^h	
Immunoassays																
Serum- Humoral Assays		32		32		32		32		32	32	32	32	32		32
PBMC Cellular Assays & plasma		64*		64*		64*	64		64	64	64	64	64		64	
Daily Volume (mL)		96		96		96	96		96	32	96	96	96		96	
Cumulative Volume (mL)		96		192		192	384		480	512	608	704	800			

^a Optional screening visit – informed consent and height/weight only performed at screening or Day 1

^b Telephone visit

^c EUA-dosing with 28-day interval – new constructs may be added as EUA is awarded and vaccine available

^d Delayed booster dose will be the 50 mcg dose of Moderna mRNA-1273. It will be administered on study day 1B which is 181 days with a window of +28 days after the second vaccine dose. If no booster administered; safety visits will continue as per [Table 6](#). If Covid-19 infection is detected in the interval between the primary series and the estimated time of booster administration, volunteers may remain in the study (with a minimum 28 day interval between infection and boost)

^e Vital signs before and after vaccination. Otherwise, only as clinically indicated.

^f For women of childbearing potential, a negative urine pregnancy test on Days 1 and 1B (delayed boost) will be performed with negative results confirmed prior to each dosing

^g Review 7-day Memory Aid data for delayed booster dose.

^h Collect nasal or NP swabs (x 2) for PCR. Sequencing will be performed on all illness visit-confirmed SARS-CoV-2 specimens.

*Collection of PBMC for cellular assays is performed at the discretion of the site, based on the capacity for PBMC processing

Table 5: SOA for Prospective Cohort 2 (2nd booster dose)

Study Day		1C	8C ^b	15C	29C	91C	181C	Illness/Unsch Visit	Early Term Visit
Visit Number		13	14	15	16	17	18		
Window (+/-)		0	1	2	2	7	14		
Informed Consent		X							
Eligibility Criteria		X							
Vaccination		X ^a							
Concomitant Meds		X	X	X	X				
Interim History		X	X	X	X	X	X	X	X
Physical Exam - Targeted		X		X	X	X	X	X	X
Vital Signs ^c		X		X	X			X	
Saliva Mucosal Sample		X		X	X	X	X		X
Nasal Mucosal Sample		X		X	X	X	X		X
Urine β-HCG ^d		X							
Memory Aid, Solicited AEs	Boost to occur ≥ 120 days and ≤ 366 days from Dose 3	X	X	X ^e					
Unsolicited AEs		X	X	X	X				
SAEs, Protocol specified AESIs, MAAEs, and NOCMCs		X	X	X	X	X	X	X	X
Nasal or NP swab for PCR & Sequencing								X ^f	
Immunoassays									

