infection. They will be assigned to receive COVID-19 vaccine under EUA dosing (as programmatically outlined in Table 9. Additional pools of subjects can be included if needed as additional COVID-19 vaccines are awarded EUA. These pools of participants were to be assigned a novel homologous or heterologous variant boost or heterologous platform boost at a minimum of 12 weeks following receipt of EUA dosing and followed through 12 months after the last vaccination. As booster vaccines have been approved for individuals at an interval of 6 months from the primary series, under EUA, all Cohort 2 volunteers will be offered a booster of mRNA-1273 at the approved 50 mcg dose at Day 181 (+/- 30 days following dose 2 of their primary series. A telephone visit will occur one week after each primary EUA vaccination and one week after the booster dose. In person follow-up visits will occur on 14 days following completion of EUA vaccinations and on days 14, and 28 days after the booster dose, as well as 3, 6, and 12 months post the booster vaccination. A fourth dose of COVID-19 vaccine will be administered to participants using the Moderna mRNA-1273.222 bivalent vaccine at an interval of 4 to 12 months after the third dose (1st booster). In addition to the other immunologic assays planned for earlier parts of the study (including innate, cellular and humoral responses), samples also will be collected to measure mucosal immune responses before the booster dose and on days 14 and 28, and at 3 months and 6 months after the fourth dose (2nd booster). Due to the surge of the Omicron variant and breakthrough infections, volunteers who contract symptomatic or asymptomatic COVID-19 between completion of their EUA primary series and the scheduled booster dose will be allowed to continue in the study. The interval between the COVID-19 infection and booster dosing should be a minimum of 28 days.

Table 9: Cohort 2 Treatment Arms

Group	Sample Size	First Vaccination	Second Vaccination		Booster Vaccination 1		Booster Vaccination 2	
		Product and Dose	Interval	Product and Dose	Interval	Product and Dose	Interval	Product and Dose
1	250	100 mcg mRNA-1273	28 days	100 mcg mRNA-1273	~6 months	50 mcg mRNA-1273	4-12 months	50 mcg mRNA-1273.222

For both Cohorts 1 and 2, reactogenicity will be assessed at the above-mentioned visits and blood will be drawn for immunogenicity assays at the in-person follow-up visits.

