7.1.3 Discontinuation of Study Intervention

For Cohort 2, prior to receiving the second and third vaccination, subjects will be reassessed. The following events constitute contraindications to any further administration of study vaccines. If any of these events occur during the study prior to the second vaccination, the subject must not receive the second vaccination but will be encouraged to continue study participation for safety and immunogenicity evaluations through 12 months after their last vaccination. For Cohort 2, if any of these events occur after the second vaccination and before the third vaccination the subject must not receive the third vaccination but will be encouraged to continue study participation for safety and immunogenicity evaluations through 12 months after their last study vaccination. See **Table 5** for a schedule of evaluations in the 12 months after the last study vaccination.

- Any clinically significant medical condition that, in the opinion of the participating site PI or appropriate sub-investigator, poses an additional risk to the subject if he/she continues to participate in the study.
- Confirmed SARS-CoV-2 infection (prior to Dose 2).
- Receipt of SARS-CoV-2 vaccine outside of study
- Anaphylaxis or unexpected systemic hypersensitivity reaction following the administration of a prior study vaccination.
- Any SAE judged to be related to vaccine.
- Pregnancy.
- New information becomes available that makes further participation unsafe or interferes with the evaluation of responses.
- Termination of this trial.

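### Protocol 9.4.9 plans the mucosal antibody analyses only after the second boost and does not use the scheduled pre-dose (1C) sample, so they show no change from before that boost

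*Protocol*

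**What the plan says.** The mucosal objective applies to Cohort 2 participants who receive the second boost. Three parts of the protocol bear on it.

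- **Analysis.** Section 9.4.9 says that mucosal responses from nasal and salivary samples "will be summarized at each timepoint post-boost" and that "the correlation between the mucosal and the serological immune responses will be evaluated at each timepoint post-boost". It names no 1C summary, fold rise or baseline adjustment. In the same section, B-cell and T-cell results are summarised at every timepoint, so the narrower wording is particular to the mucosal samples.
- **Sampling.** Section 4.1 says "samples also will be collected to measure mucosal immune responses before the booster dose and on days 14 and 28", with further samples at 3 and 6 months. In Table 5 the rows for saliva and for "Nasal Mucosal Sample" are marked at 1C, 15C, 29C, 91C and 181C. Table 12 schedules serum at the same five visits.
- **Prior exposure.** By 1C a participant has had two primary doses and a first booster. The Synopsis adds that "volunteers who contract symptomatic or asymptomatic COVID-19 between completion of their EUA primary series and the scheduled booster dose will be allowed to continue". Section 7.1.3 treats confirmed infection as a bar to further dosing only when it occurs before Dose 2.

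On infection, 9.4.9 goes on to say: "The possibility of conducting these analysis by status of prior infection (as given by N-protein ELISA assay) will be assessed".

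**The concern.** The stated objective is to assess mucosal IgG and IgA responses, and the Synopsis follows this pool to learn about the immunogenicity of the fourth dose. Cohort 2 has one group. Those who do not take the second boost move to the Table 6 schedule, which has no mucosal sampling, so there is no unboosted comparator. Within the trial's own data, the change within a person from 1C is therefore the only direct view of what happened to mucosal antibody across the second boost, and the protocol does not plan to report it.

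Post-boost levels may contain antibody left from three doses and from infections that the protocol permits. The same holds for the mucosal-serum correlation. People with stronger earlier exposure may be high in both compartments whatever the second boost did.

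For serum, section 9.4.3 does plan a fold rise from baseline, although it does not say which visit is the baseline for the second boost in Cohort 2.

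**Working it through.** The documents give no sample size, SD or precision for the mucosal analysis, so there is no stated figure to reproduce. The check compares the passages and then illustrates the mechanism with assumed inputs.

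**1. Sampled against analysed (Cohort 2, second boost)**

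| Visit | Mucosal sample (Table 5) | Serum sample (Table 12) | Mucosal analysis (9.4.9) |
|---|---|---|---|
| 1C, pre-dose | yes | yes | none stated |
| 15C, 29C, 91C, 181C | yes | yes | summary and correlation |

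The paired baseline is scheduled in both compartments and unused in the planned analysis.

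**2. What a level alone shows.** Take a hypothetical post-boost geometric mean of 100. With a 1C geometric mean of 100 the rise is 100/100 = 1-fold. With a 1C geometric mean of 10 it is 100/10 = 10-fold. The planned summary would look the same in both cases.

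**3. Correlation through general carry-over.** On the log scale let post = pre + rise, with pre and rise independent. Assume that the mucosal and serum rises are uncorrelated. Let r0 be the pre-boost mucosal-serum correlation, and let f = Var(pre)/Var(post), taken as equal in both compartments. The covariance of the post-boost values is then that of the pre-boost values, so corr(post) = f × r0.

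| r0 (assumed) | f = 0.25 | f = 0.50 | f = 0.75 |
|---|---|---|---|
| 0.3 | 0.075 | 0.150 | 0.225 |
| 0.5 | 0.125 | 0.250 | 0.375 |
| 0.7 | 0.175 | 0.350 | 0.525 |

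A simulation of 200,000 pairs at r0 = 0.5 and f = 0.5 gave 0.247 for post-boost levels (formula: 0.250) and -0.002 for the rises (true value: 0).

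**4. Correlation through prior infection alone.** Suppose a share p was infected before 1C, infection multiplies both compartments by s, and the residual log SD is sd with no residual correlation. Then corr(post) = p(1-p)ln(s)² / [p(1-p)ln(s)² + sd²].

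- p = 0.4, s = 4, sd = 0.8: 0.24 × 1.92 = 0.46, and 0.46/(0.46 + 0.64) = 0.42.
- p = 0.2, s = 4, sd = 1.0: 0.16 × 1.92 = 0.307, and 0.307/1.307 = 0.24.
- s = 2 with the same two pairs of p and sd: 0.115/(0.115 + 0.64) = 0.15 and 0.077/1.077 = 0.07.

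**5. What display by N-protein status would do.** In step 4 the correlation within each infection stratum is 0, so stratifying would remove it if N-protein classified everyone correctly. In step 3, where the shared component comes from earlier vaccination, stratifying by infection leaves f × r0 in place.

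**The case against.** Several points on the other side have force.

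- **The endpoint is a level.** Table 7 defines it as magnitude, percentage and correlation with serum, and section 8.1.2 says the same of the assay results. Whether serum level tracks mucosal level is a fair question, and shared exposure is part of the answer. This stands. It is a reason to keep the same-visit correlation as the stated endpoint rather than replace it. It does not explain leaving out the 1C row.
- **The Cohort 2 SAP is not in hand.** SAP 2.1 gives Cohort 2 its own report and SAP, and the supplied SAP covers only groups 4E, 5E and 6E. The missing SAP may already specify a comparison with 1C. This limits the point to the protocol text. Section 9.4.9 does not defer the matter to the SAP, as 9.4.7 does for subgroups.
- **Infection is already considered.** It is, but only as a possibility to be assessed, and step 5 shows that it leaves vaccine carry-over untouched.
- **Fold rises have faults of their own.** A difference of two assay values carries more error. If infected people start high and rise less in both compartments, infection also induces a correlation between the rises. Infection after 1C is not removed either. All of this stands, and it is why the correlation of rises is only supplementary.
- **The stakes are low.** The analysis is exploratory, uses at least a subset of samples, and tests no hypothesis. This is true, and it limits how much weight the point can carry.

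A reader might go further and infer that carry-over cannot be separated from the boost response. The documents do not support that: the 1C saliva, nasal and serum samples are scheduled and individual data will be listed (9.4.8), so a paired comparison is possible and merely unplanned. Nor do they show that mucosal antibody is present at 1C. That is an expectation in this population, and the documents contain no mucosal data.

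**Conclusion.** The concern holds as a gap in the protocol's exploratory plan. Section 9.4.9 confines both mucosal analyses to visits after the second boost, while sections 1.2 and 4.1 schedule the pre-dose sample that would show change across that boost. Without it, the planned output can neither show nor rule out a mucosal response to the second boost.

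The size is unknown. The correlations of 0.07 to 0.525 rest wholly on assumed values of r0, f, p, s and sd, on uncorrelated rises, and on equal carry-over or an equal infection effect in the two compartments. They show that a same-visit correlation need not reflect the second boost. They do not predict what this trial will find, and they give no ground for saying that an observed correlation would come entirely from prior infection. The conclusion concerns the protocol as written. The Cohort 2 SAP was not available and could close the gap.

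**What to change.** In Protocol 9.4.9, and in the Cohort 2 SAP if it does not already do so:

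1. Summarise mucosal IgG and IgA at 1C (pre-dose) and at each later visit.
2. Report the geometric mean fold rise from 1C with a 95% CI at 15C, 29C, 91C and 181C.
3. Keep the same-visit mucosal-serum correlation as the stated endpoint, and add it at 1C so that post-boost values can be read against it.
4. Add, as a supplementary display, the correlation of mucosal with serum fold rises, both taken from 1C.
5. Flag infections detected after 1C, and say whether the display by N-protein status will be produced.

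The cost is a few sentences and some extra table rows, with no new samples or visits. Participants without a usable 1C sample drop out of the fold-rise summaries, so the number contributing should be shown. The fold-rise correlations will be noisier than the same-visit ones. Change from 1C in a single group still does not separate the boost from an infection after 1C, which is why those infections need flagging.
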